The StepRite system developed by MedHab (<http://www.medhab.com/>) allows the physical therapist to monitor physical activity and exercise remotely, thereby reducing the need for frequent out-patient visits. A thin insole placed inside the shoe measures foot contact pressure and acceleration. This information is translated into quantitative feedback about exercise compliance and performance measures comparing the surgical side with the non-surgical side. Real time feedback during exercise and weight-bearing activities is

provided to the patient, and a HIPAA secured user interface website also displays this information in an online dashboard for both physical therapists and the physician.

With the advent of federally mandated bundled payments for total joint replacement, active management of the rehabilitative process postoperatively with quantifiable data will be necessary to ensure financial stability.

Given the potential for improving patient engagement with rehabilitation, this study proposes a treatment model which includes monitoring activity outside of the clinic using the StepRite device and using a combination of outpatient appointments and remote consultations with therapists.

Significance of this study

The significance of the proposed study includes the projected benefit to the patients in terms of attaining clinical outcomes quicker and to the medical system in terms of managing cost for the provision of services. Subjects are expected to demonstrate improved compliance to patient tailored rehabilitation protocols which will lead to more rapid attainment of clinical outcomes versus present traditional rehabilitation methodologies. The expected level of, and rate of, attainment of clinical outcomes will translate to an overall reduction of cost to the medical system by reducing the need to engage in additional processes or the need to protract the time required to attain clinical outcomes, where either or both in combination can increase rehabilitation expenditures.

Objectives

To compare the efficacy of StepRite in a prescribed physical therapy program verses traditional in-facility physical therapy program after partial or primary total knee replacement using validated survey tools to evaluate patient progress, including patient self-reporting of progress and surgeon appraisal of patient performance post-operatively.

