To compare the overall cost of post-operative rehabilitation of patients involved in traditionally employed regimens versus those using the StepRite device.

Hypothesis and specific aims

The aim of this study is to evaluate whether improved clinical outcomes as well as reduction in cost in provision of care can be better affected through the use of the Steprite device as compared to the use of traditional rehabilitation modalities.

We will seek to reject the null hypotheses that 1) there is no difference between clinical outcomes attained between patients using the Steprite device and those using traditional rehabilitation modalities and that 2) there is no reduction in cost to the medical system when patients use Steprite versus other conventional methods of rehabilitation.

By rejecting the null hypothesis we will accept the alternate hypothesis that, through the use of the Steprite device, not only will patients achieve overall clinical outcomes faster but there will be an associated decrease in cost burden to the medical system and the differences observed will be statistically significant as compared to rehabilitation of patients not using the Steprite device.

Patients who use the device post-surgery will demonstrate superior short-term improvements (i.e. 3 months post-surgery) with respect to self-reported functional outcomes and gait parameters, compared to a control group not using the device. The patients will self-report through the use of validated survey instruments including the KOOS survey (knee injury and osteoarthritis outcome score), LEFS (lower extremity functional scale) and/or KSS (knee society score), the latter of which includes a section for surgeon evaluation of patient functionality post operatively.

Study Design and Methods

This is a point of care clinical trial; a trial that functions to integrate research within a clinical setting that has the ability to readily deliver either modality of the proposal. This type of study design relies on provider referral of patients to be approached for consent, after which randomization to one of two treatment groups is facilitated; a control group of 15 patients participating in conventional rehabilitation regimens and an experimental group of 15 patients who will participate in the same rehabilitation regimen but facilitated

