through the use of Steprite. Importantly, care for patients is delivered as part of current adopted standards utilizing outcome measurements, the use of which and the interpretation of which is already built into care provided by the clinical facility, thereby negating the need to develop additional outcome measures. Recruitment of 30 patients will come from the investigators' normal patient population, among patients who are scheduled for partial or total knee arthroplasty. As there is no change in post op care for these patients from the investigators standard protocols other than monitoring and enforcement of home protocols, the same therapists involved in investigators' normal patient care will be involved with both arms of the study.

For this study, 30 patients represents a sample size deemed acceptable as a starting point. There are no other published studies using Steprite in comparative design trials. Determinations of sample size needed for this study, using 80% power and significance of 0.05, incorporate the use of a time frame in days or weeks for completion of the rehabilitation protocols that would allow for the detection of clinically significant differences between the group using Steprite and those using conventional therapies only. Given that conventional therapies can include skilled nursing, home health and outpatient visits and given that the need for each of these is highly variable dependent on the patient, it is difficult to assign a time value for determinations of sample size.

With that, a sample size of 30 participants divided into two groups represents an initial starting point, with the potential of incremental addition of more patients in order to achieve significance between the two study groups.

Statistical significance will be evaluated utilizing a standard t-test for two group comparison.

In preparation for the study, MedHab Inc. will at their expense train all involved investigators and therapists in the fitting and use of the StepRite device. Medhab will also train a lead therapist designated by the lead investigator to be in charge of overseeing and monitoring, ensuring proper use of the device. There is no cost to the patient, hospital or other funding entity for participation in this study. Medhab LLC will assume all costs associated with the training, application, device and use of the StepRite product for the full course of this study.

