There is a risk of loss of confidentiality, we will have measures in place to help prevent any loss of personal information. During the course of this study there are no new or additional steps required of the subjects from what is considered the standard protocol for the lead investigator. The only alteration may be reduced travel and outpatient visit by the patient if compliance and functional improvement noted by the therapist. StepRite imparts no energy to the patient and poses no hazard to patient well being. Subjects will be free to withdraw from the study at any time and revert to conventional rehabilitation treatment.

Possible benefits to subjects

There is a possibility the device group patient could benefit from the device prompting them to do their own exercises regularly, which could lead to a faster recovery and better physical therapy outcomes. We are hoping the participation in this study may help us learn how we can design rehabilitation programs to be more effective in the future.

Confidentiality measures

StepRite / MedHab will have access to non-PHI patient data collected by the device stored on their HIPPA compliant server and be available only to the lead investigator. All PHI will be kept separate from the study data in a locked filing cabinet or on a password protected computer in the research coordinators office in 4A144B.

Data Collection and Monitoring

Data recorded by the StepRite device will be transmitted wirelessly to the HIPAA secured web interface managed by Medhab. Clinicians will be able to log into the website with a password to review the progress of each patient.

Data recorded by the PI and physical therapist on the functional motion of the knee will be recorded in paper form and kept with the completed KOOS questionnaire and Knee Society Score (KSS) and scanned into the patients HIPPA protected chart.

Upon completion of patient's part in the study MedHab will contact UMC and the Therapy departments to acquire actual costs of these services. This will be done to compare the overall cost of management of the post-operative rehabilitation of a patient in traditional rehabilitative regimen vs. use of StepRite,

Actual Cost information for the patient's full rehabilitation will be requested and collected by the Hospital and released to MedHab at the end of the study and supplied to the lead investigator for analysis.

References

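### The cost claim is made for the medical system, but the items to be counted are undefined, nothing charges the device's own cost to the device arm, and the data reach the analyst through the manufacturer

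*Combined protocol and SAP*

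**What the plan says.** Cost is one of the protocol's two objectives: "To compare the overall cost of post-operative rehabilitation of patients involved in traditionally employed regimens versus those using the StepRite device" (Objectives). The matching null hypothesis is worded more broadly: "there is no reduction in cost to the medical system when patients use Steprite versus other conventional methods of rehabilitation" (Hypothesis and specific aims). Significance of this study links the two, arguing that faster attainment of outcomes "will translate to an overall reduction of cost to the medical system" through lower rehabilitation spending.

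On the care that generates cost, Study Design and Methods says that "conventional therapies can include skilled nursing, home health and outpatient visits", with need varying widely between patients. Schedule of events gives both arms outpatient, home health and/or 24-hour therapy plans, and mentions home visits and telephone consultations.

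On the cost data, Data Collection and Monitoring makes two statements. The first is that, once a patient has finished, "MedHab will contact UMC and the Therapy departments to acquire actual costs of these services". The second is that cost information for the patient's whole rehabilitation "will be requested and collected by the Hospital and released to MedHab at the end of the study and supplied to the lead investigator", who analyses it.

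Study Design and Methods also has MedHab pay for the device, the app, the training and the use of the product throughout the study.

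**The concern.** A claim about cost to the medical system needs a stated list of what is counted, applied equally to both arms, and it needs the cost of the intervention itself. The protocol gives no list of items, no perspective and no time window. The device arm receives something the control arm does not, and its price appears nowhere in the comparison. A health system that adopted the device might have to bear that price.

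The data for this objective also pass through the company that makes the device before the investigator sees them. At stake is whether a reported saving could be taken at face value by someone deciding whether to pay for the device.

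**Working it through.** The plan states no cost figure, so there is nothing to reproduce. The check is mainly a comparison of the text, with one illustration under assumptions.

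**1. Items of care against named cost sources**

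| Item | Where it appears | Named as a cost source? |
|---|---|---|
| Hospital | Data Collection and Monitoring | Yes (UMC) |
| Outpatient therapy | Schedule of events | Yes (therapy departments) |
| Telephone consultations | Schedule of events, given by the outpatient therapists | Not separately; would ordinarily fall under the therapy departments |
| Home health | Study Design and Methods; Schedule of events | No; may fall within full rehabilitation |
| Skilled nursing | Study Design and Methods | No; may fall within full rehabilitation |
| Device, app, training | Study Design and Methods, paid by MedHab | No, and not charged to the device arm |

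The coverage of home health and skilled nursing depends on what the second statement includes. The text does not say.

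**2. The device's own cost**

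Let S be the mean counted cost in the control arm minus that in the device arm, and D the cost per patient of device, app and training at a stated price. The plan as written reports S. The saving with the intervention counted is S − D. Whenever 0 < S < D, the plan reports a saving where total cost rose. Neither S nor D can be obtained from the documents.

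*Illustration.* Assume that true total costs are equal (so S = D), that D is the same for every device patient and equals b standard deviations of cost, and that costs are roughly normal with equal variance. The plan's t-test with n = 15 per arm has 2 × 15 − 2 = 28 degrees of freedom. I assume a two-sided 0.05 level, since sidedness is not stated. The noncentrality is b × √(15/2) = 2.739b.

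| b (assumed) | Noncentrality | Rejection rate |
|---|---|---|
| 0 | 0 | 5.0% |
| 0.10 | 0.27 | 5.8% |
| 0.25 | 0.68 | 10.1% |
| 0.50 | 1.37 | 26.2% |
| 1.00 | 2.74 | 75.3% |

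No value of b has support in the documents. The table shows only that the harm is slight if the device is cheap relative to the spread of costs, and large if it is not.

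**3. The route of the data**

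| | First statement | Second statement |
|---|---|---|
| Who requests | MedHab | The Hospital |
| From whom | UMC and therapy departments | Not stated |
| Scope | The services of those departments | Full rehabilitation |
| When | After each patient's part is complete | Released at the end of the study |
| Path | To MedHab | Hospital, then MedHab, then lead investigator |

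MedHab handles the data on either account. Device Information identifies it as manufacturer and supplier. The Device Flow Chart has it share with the investigator in extending or closing therapy, which can affect cost. The site description says that it will compare cost across several sites. No direct transfer, blinding, data lock or independent check of the cost data is described.

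**The case against.** The strongest reply is that the protocol does ask for complete costs. It says that cost information for the patient's "full rehabilitation will be requested and collected by the Hospital", and requesting suggests obtaining costs from others, not merely reading the Hospital's own ledger. The stated objective is rehabilitation cost, which is narrower than every cost to the medical system. The two data statements can be read as one chain: MedHab makes contact, the Hospital collects and releases, the investigator analyses. Much of this stands, and it rules out several stronger readings:

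- A reader might infer that home health and skilled nursing are left out and that the comparison is therefore partial. The documents show that coverage is unspecified, not that these costs are excluded.
- A reader might infer that the device moves care into home health, where it goes uncounted. Nothing says so. Both arms have the same range of therapy plans, and Risks mentions only possibly reduced travel and outpatient visits. Remote contacts belong to therapists whose departments are a named source.
- A reader might infer that the manufacturer will bias the result. Analysis is assigned to the lead investigator, and no distortion is shown.

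The reply leaves three things unanswered: the treatment of device and training cost, the differing requester and timing, and the absence of any safeguard on data passing through an interested party. That the study costs patients and the hospital nothing is a statement about who pays during the trial. It does not make the device free to a system that later adopts it.

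**Conclusion.** The concern holds in a limited form. The hypothesis is about the medical system, while the only providers named as cost sources are UMC and the therapy departments, and the content of full rehabilitation cost is undefined. A comparison run exactly as written can report a saving that omits the intervention's own cost. The data path gives the manufacturer an intermediary role with no described check, which is a risk of bias and no more than that.

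The size cannot be determined from the documents. Section 2 of the working shows only how the answer would depend on an assumed device cost. The omission of device cost rests on the plan's silence; a separate costing document, if one exists, could settle it. This should be corrected because the remedy is cheap. It does not by itself invalidate the trial.

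**What to change.** Replace the two statements in Data Collection and Monitoring with one rule:

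- For every patient in both arms, collect the same cost items over the same fixed window: hospital, outpatient therapy including remote contacts, home health and skilled nursing.
- The Hospital and the other providers send these directly to the lead investigator. MedHab receives them only after the analysis file is locked.
- Report the comparison with device and training cost added to the device arm at a stated price.
- If outside-provider or device costs cannot be obtained, word the conclusion for the items actually counted, not for the medical system.

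The price is a protocol wording change and additional cost requests for about 30 patients. Obtaining figures from outside providers may take some effort. The fallback of a narrower conclusion needs no extra data but gives up part of the stated cost objective. The cost result may also look less favourable to the device.
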